10.5.2 Physical Exam and Adverse Events

Physical exam results will be summarized by frequency of presence of abnormalities in body system (beyond the DMD diagnosis) and in particular any changes in the physical exam over time. Any new adverse events (AEs) occurring after the time of enrollment into NS-065/NCNP-01-202 (defined as the time of IP infusion at the Week 25 visit) will be considered for analysis for this study. For AEs starting in study NS-065/NCNP-01-201 which are not resolved at the time of enrollment into NS-065/NCNP-01-202, any change in outcome or relatedness will be reported in study NS-065/NCNP-01-201. For AEs starting in study NS-065/NCNP-01-201 which increase in severity or becomes serious after enrollment in study NS-065/NCNP-01-202, a new AE will be reported in NS-065/NCNP-01-202.

Treatment-emergent AEs (TEAEs) will be summarized by dose level. Coding will be done by system organ class and preferred term (using the Medical Dictionary for Regulatory Activities (MedDRA)). Level of severity will be assessed using the CTCAE grading system. Summaries will include:

A. Summaries at the patient level

How many patients had any TEAE, any SAE, highest severity of TEAE within a patient across all infusions, highest relationship level of TEAE within a patient across all infusions, highest intervention level regarding investigational product (e.g., discontinued, vs. reduced dose vs. temporarily stopped vs. no interruption in infusions), and worst outcome within a patient (e.g., AE did not resolve and has a permanent effect).

B. Summary at the event level

Summaries will be done using the MedDRA coding by events and overall, summarizing by system organ class and preferred term, by relationship to investigational product, severity, intervention, and outcome.

Listings tables will be provided for all AEs.

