Test Product, Dose, and Mode of Administration	
NS-065/NCNP-01 Injection 250 mg aqueous infusions will be supplied as a 10-mL or 5-mL glass vial containing 25 mg/mL or 50 mg/mL of drug product in saline, respectively.
 
Patients will begin dosing in this study at the same dose level they received in Study NS-065/NCNP-01-201. Once sites receive IRB approval of Protocol Amendment 10, all subjects who were previously in the low dose cohort of 40mg/kg/week will receive 80mg/kg/week after obtaining patient consent/assent. Patients will continue at dose level of up to 80 mg/kg/week for the remaining duration of the trial, up to 192-week (up to a total of 216 weeks of treatment in Study NS-065/NCNP-01-201 and 202) extension study or enrollment in a separate long-term follow up program of NS-065/NCNP-01, whichever is earlier.
 
Investigational product will be prepared in accordance with an Investigational Product Instruction Manual (IPIM) and administered by intravenous infusion over a 1-hour period.

Safety Assessments	
 1. Overall incidence of adverse events (AEs) and serious adverse events (SAEs) 2. Changes from baseline compared to Screening Visit and Week 25 of Study NS-065/NCNP-01-201 in laboratory parameters (blood, urine). 3. Changes from baseline compared to Day 1 and Week 25 of Study NS-065/NCNP-01-201 in electrocardiograms (ECGs), anthropometrics, vital signs, and diagnostic parameters (physical exam). 4. Anti-NS-065/NCNP-01 antibodies at Weeks 37, 49, 73, 97, 121, 145, 169, 193 and 217 compared to Day 1 and Week 24 of Study NS-065/NCNP-01-201. 5. Anti-dystrophin antibodies at Weeks 37, 49, 73, 97, 121, 145, 169, 193 and 217 compared to Day 1 and Week 24 of Study NS-065/NCNP-01-201. 6. Cytokine levels at Weeks 37, 49, 73, and 97 compared to Day 1 and Week 24 of Study NS-065/NCNP-01-201.
Efficacy Assessments	
Primary:
 
Time to Stand (TTSTAND) at 37, 49, 61, 73, 85, 97, 109, 121, 133, 145, 157, 169, 181, 193, 205 and 217 Weeks compared to Pre-Infusion Visit and Week 25 of Study NS-065/NCNP-01-201.
 
Secondary:

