2. STUDY OBJECTIVES

2.1. Primary Objectives

1. To evaluate the safety and tolerability of low (40 mg/kg/week) and high (80 mg/kg/week) IV doses of NS-065/NCNP-01 Injection up to 192-week Treatment Period (up to a total of 216 weeks of treatment in Study NS-065/NCNP-01-201 and 202), in boys with DMD completing Study NS-065/NCNP-01-201.
2. To investigate the effect of low and high IV doses of NS-065/NCNP-01 Injection after an additional up to 192-week Treatment Period (up to a total of 216 weeks of treatment in Study NS-065/NCNP-01-201 and 202) on muscle strength, mobility, and functional exercise capacity, as measured by Time to Stand (TTSTAND), in boys with DMD who complete Study NS-065/NCNP-01-201 vs. matched historical controls in boys with DMD.

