9. SAFETY PROCEDURES AND PROCESSES

9.1. Definition of an Adverse Event

An AE is any untoward medical occurrence in a patient or clinical investigation patient administered a pharmaceutical product, including control, and which does not necessarily have a causal relationship with treatment. This includes any untoward signs or symptoms experienced by the patient from the time of consent until completion of the study.

AEs may include, but are not limited to:

- Any unfavorable and unintended sign (including an abnormal laboratory finding), symptom, or disease temporally associated with the use of a medicinal product, whether or not considered related to the medicinal product.
- Any new disease or exacerbation of an existing disease.
- Any deterioration in non-protocol-required measurements of laboratory value or other clinical test (e.g., ECG) that results in symptoms, a change in treatment, or discontinuation from investigational product.

Disease signs, symptoms, and/or laboratory abnormalities already existing prior to the use of the product are not considered AEs after treatment, unless they reoccur after the patient has recovered from the preexisting condition or in the opinion of the Investigator they represent a clinically significant exacerbation in intensity or frequency. If clinically significant worsening from baseline is noted, the changes will be documented in the AE source document and the eCRF.

Treatment-emergent adverse events (TEAEs) are defined as any adverse event or worsening of an existing condition after initiation of the investigational product and through 30 days following the last dose of investigational product.

Suspected adverse reaction means any AE for which there is a reasonable possibility that the drug caused the AE. For the purposes of IND safety reporting, ‘reasonable possibility’ means there is evidence to suggest a causal relationship between the drug and the AE. A suspected adverse reaction implies a lesser degree of certainty about causality than adverse reaction, which means any adverse event caused by a drug.

An AE or suspected adverse reaction is considered “unexpected” if it is not listed in the Investigator’s Brochure or is not listed at the specificity or severity that has been previously observed. During the course of the study, the Investigator’s Brochure should be updated on an ongoing basis with new important safety information.

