10.5.1 Anthropometrics, Vital Signs, Laboratory Assessments, and ECG

Anthropometrics, vital signs, hematology, chemistry, BNP, urinalysis, and ECG results will be summarized by dose level over time using descriptive statistics for continuous outcomes. Actual values and change from Screening Visit (hematology, chemistry and urinalysis) or Day 1 (anthropometrics, vital signs and ECG) from Study NS-065/NCNP-01-201 and change from Week 25 (baseline of the NS-065/NCNP-01-202 study) will be presented. Further, all lab abnormalities will be listed.

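### Section 10.5.2 describes no adverse-event summary over the cumulative 216 weeks, and late changes to events carried over from Study 201 do not enter the Study 202 tables

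*Combined protocol and SAP*

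**What the plan says.** - **Objective (Section 2.1).** Safety and tolerability are to be evaluated over an "up to 192-week Treatment Period (up to a total of 216 weeks of treatment in Study NS-065/NCNP-01-201 and 202". Section 10.5 calls this one of two co-primary objectives.
- **Event window (Section 10.5.2).** The analysis takes "Any new adverse events (AEs) occurring after the time of enrollment into NS-065/NCNP-01-202", and enrollment is "defined as the time of IP infusion at the Week 25 visit) will be considered for analysis for this study".
- **Carried-over events (Section 10.5.2).** For Study 201 events still unresolved at that point, "any change in outcome or relatedness will be reported in study NS-065/NCNP-01-201". The exception is an event that worsens or turns serious: for those that "increase in severity or becomes serious after enrollment in study NS-065/NCNP-01-202, a new AE will be reported in NS-065/NCNP-01-202".
- **TEAE definition (Section 9.1).** A TEAE is "any adverse event or worsening of an existing condition after initiation of the investigational product and through 30 days following the last dose". The section does not say which study's first dose is meant.
- **Other safety data.** Section 10.5.1 presents "Actual values and change from Screening Visit (hematology, chemistry and urinalysis) or Day 1 (anthropometrics, vital signs and ECG) from Study NS-065/NCNP-01-201", and also change from Week 25. The synopsis has both antibody assays at Weeks 37 to "169, 193 and 217 compared to Day 1 and Week 24 of Study NS-065/NCNP-01-201".
- **Population (Section 10.3).** The Safety Population requires at least one dose in each study.
- **Status of Study 201 (Appendix 3, Amendment 8).** The log gives completion of Study 201 as its reason for a text change.

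**The concern.** Most of the planned analysis looks across both studies. The population requires dosing in both, and laboratory, vital-sign, ECG and efficacy results are each shown against a Study 201 baseline and against Week 25. Adverse events have a single window that starts at Week 25.

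Two things follow if Section 10.5.2 is applied as written. First, there is no described count or rate of adverse events over the cumulative exposure that the objective cites. An event that began in Study 201 and persists without worsening is not new, so it does not count towards Study 202 incidence. Second, the patient-level summaries in Section 10.5.2 include the strongest relationship to drug and the worst outcome for each boy. Those are the two attributes whose later changes are sent to Study 201 for carried-over events. A persistent finding judged drug-related in, say, the second year of the extension would leave the Study 202 summaries unchanged.

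The protocol's own background makes persistent early findings plausible. In the 12-week Phase I study (Section 1.3.5.1) all 10 patients had at least one adverse event, and Grade 1 anemia was seen in 7 of 10. Urine NAG rose in all 3 patients of each of the first two cohorts and in 3 of 4 in the third, so 9 of 10. Section 1.3.4 names the kidney as the primary target organ in animals.

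**Working it through.** **1. Reproduce the plan's total.** Infusions in Study 202 run weekly from Week 25 to Week 216 (Section 8.1): 216 − 25 + 1 = 192. Study 201 lasted 24 weeks (Section 1.3.5.2). 24 + 192 = 216, as Section 2.1 states.

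**2. Share outside the event window.** Study 201 weeks ÷ total weeks = 24/216 = 11.1%. The window covers 192/216 = 88.9%. For 16 boys with full follow-up, 16 × 24 = 384 of 16 × 216 = 3,456 patient-weeks lie outside.

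**3. Counting active drug only.** Some Study 201 participants had placebo for the first 4 weeks, so Section 1.4 speaks of 20 to 24 weeks of treatment. A boy who had placebo contributes 20/(20 + 192) = 20/212 = 9.4%; one who did not contributes 24/216 = 11.1%. The range is 9.4% to 11.1%.

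**4. Weight of one boy.** With 16 boys, one whose classification changes moves a patient-level proportion by 1/16 = 6.25 percentage points. By dose level, assuming 8 per group, it is 1/8 = 12.5 points. This is the granularity of the table, not an estimate of bias: the documents do not say how many boys had an unresolved event at Week 25.

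**5. What happens to a Study 201 event unresolved at Week 25 (Section 10.5.2).**

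| Later change | Where it is reported | In the Study 202 tables? |
|---|---|---|
| Severity increases | Study 202, as a new event | Yes |
| Becomes serious | Study 202, as a new event | Yes |
| Relatedness is revised | Study 201 | No |
| Outcome changes | Study 201 | No |
| No change | Remains a Study 201 event | No |

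No section says how the third and fourth rows would be shown in the Study 202 report.

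**6. Start of the TEAE window.** Section 9.1 starts it at initiation of investigational product. For these boys that could mean the first dose in Study 201 or the Week 25 dose. Section 7.1 starts this study's Treatment Phase with the first dose at Week 25, which supports the second reading. Section 10.5.2 also summarises severity and relationship over all of a boy's infusions without saying whether Study 201 infusions count. The text allows two different tables.

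**The case against.** The strongest reply is that the Week 25 cut is a deliberate allocation rule. Amendment 2 added it as a clarification, it assigns each event to one study, and it avoids double counting. Study 201 has its own safety purpose, so events at first exposure are reported there. Worsening and newly serious events are carried forward. This stands, and it is the reason to keep the Study 202-only table. It does not supply a cumulative summary or a route for late changes into the Study 202 report.

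Four stronger readings are tempting, and the documents do not support them.

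- **That no planned table answers the safety objective.** The objective names the 192-week period first, and the adverse-event tables cover it. The 216 weeks stand in parentheses. Laboratory, vital-sign, ECG, anthropometric and antibody results already use Study 201 baselines, and cytokines do so through Week 97.
- **That Sections 9.1 and 10.5.2 contradict each other.** Section 9.1 names no study, and Section 7.1 fits the Week 25 start. This is an ambiguity.
- **That late changes will be lost from both reports.** The log says Study 201 is completed. It does not say that its database is locked or its report final, and Section 10.5.2 positively directs updates there.
- **That the omitted weeks hold an excess of infusion-related events, or that overall incidence is materially understated.** Nothing in the documents shows the former. On the latter, every Phase I patient had an event within 12 weeks, so the share of boys with any event over 192 weeks may be close to its ceiling in either table. The summaries of related events and of outcome are the more exposed ones.

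Section 10.1 also defers detail to a SAP that overrides the protocol. No separate SAP text was supplied, so a cumulative table may be planned there.

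**Conclusion.** The point holds in a limited form. On the protocol as written, adverse-event summaries leave out the 24 Study 201 weeks, 11.1% of the cumulative 216 (9.4% to 11.1% on active drug). The Study 202 summaries of strongest relationship and worst outcome do not reflect later changes to carried-over events. The effect on any reported proportion is unknown; each affected boy would shift it by 6.25 points among 16.

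The percentages assume full follow-up to Week 216. Whether the objective requires all 216 weeks to be tabulated depends on how its parenthesis is read, but the routing of late changes and the unclear TEAE start need attention on either reading. The correction is inexpensive and gives a more complete answer to a co-primary objective, so it is worth making.

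**What to change.** In Section 10.5.2, and in the SAP before database lock:

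1. Keep the Study 202-only TEAE table.
2. Add an integrated 201+202 TEAE summary from each boy's first active dose to 30 days after his last dose, with exposure-adjusted rates. Count each carried-over event once, at its worst severity, latest relatedness and final outcome, so that an event re-entered in Study 202 after worsening is not counted twice.
3. List the carried-over Study 201 events in the Study 202 report, with later changes in outcome and relatedness.

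In Section 9.1, state which first dose starts the TEAE window for each table.

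The cost is one small integrated dataset and a few tables. Patients keep their Study 201 identification numbers (Section 7.3), so linking the records is straightforward. Reported incidence may rise slightly.

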1.3.5. Summary of Clinical Findings

1.3.5.1. Phase I

A Phase I investigator-initiated study of NS-065/NCNP-01 Injection was conducted in DMD patients (aged 5-18 years) to investigate the overall usefulness of NS-065/NCNP-01 Injection in the treatment of DMD, based on evaluations of safety, exploration of predictive markers of treatment response, and assessment of pharmacokinetics. A total of 10 DMD patients were enrolled and randomized. IV administration of NS-065/NCNP-01 Injection in doses of 1.25 mg/kg, 5 mg/kg and 20 mg/kg to DMD patients once weekly for 12 weeks was well tolerated, and no

dose-limiting toxicity was observed, although all patients had at least one AE. Moreover, neither serious adverse events (SAE) nor incidences of Common Terminology Criteria for Adverse Events (CTCAE) v4.03 Grade 3 (severe) or worse were reported.

Among the mild and moderate AEs, an increase in urine beta-N-acetyl-D-glucosaminidase (Grade 1) was found in all patients in both cohorts 1 and 2 [Cohort 1 (n=3) Cohort 2 (n=3)] and in all but one patient in Cohort 3 [Cohort 3 (n=4)].

Initially, testing appeared to reveal proteinuria in 8 of 10 patients. However, it was subsequently determined that there was a cross reaction between NS-065/NCNP-01 and the pyrogallol red dye-binding method which was used for urinary protein measurement resulting in a false positive result for protein in the 24-hour pooled urine samples. To evaluate the 24-hour pooled urine samples for protein, Coomassie brilliant blue method was used to re-measure urinary protein in the frozen urine samples and none of the retested samples showed urinary protein levels exceeding the normal range of the institution (i.e., 31.2 to 120 mg/day). Current studies utilize a urine protein Benzethonium Chloride method using reagents that do not cross react with NS-065/NCNP-01. NS-065/NCNP-01 exhibited no cross reactivity with the Benzethonium Chloride Method up to 500 mg/dL.

The 24-hour pooled urine samples did not show increased levels of albumin. Spot measurements of urinary albumin were positive in 7 patients (Grade 1).

Interleukin levels were increased (Grade 1) in the serum in 6 out of 10 patients (high IL-6 level in 4 subjects, high IL-1 β level in 1 subject, and high IL-2 level in 1 subject), and some level of anemia (Grade 1) was observed in 7 out of 10 patients.

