5.5. Treatment Compliance

The patient's compliance with the treatment regimen will be monitored in terms of the patient receiving the investigational product infusion every week within a ± 3 -day window. Weekly study drug treatments for this study should be calculated from the 1st infusion of protocol NS-065/NCNP-01-201, not from the previous week's infusion. If an infusion day is rescheduled, the original scheme should be reinstated as soon as possible. Missed, delayed or incomplete infusions will be clearly documented and considered in the analysis. The amount of infusion received should be documented for all infusions.

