10.5 Safety Assessments

Safety analyses will be performed using the safety population and will address one of two co-primary objectives of the study. All safety assessments will be based on actual treatments received by participants.

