10.8 Handling of Missing Data

Every effort will be made to collect all data. However, despite best efforts, missing or incomplete data may be reported. All missing or partial data will be presented in the patient data listing, as they are recorded on the eCRF.

Patients lost to follow-up or withdrawn will be included in statistical analyses up to the point of their last evaluation. Unless otherwise specified, no imputation of values for missing data will be performed. Of note, since patients with DMD are expected to decline over time, imputing efficacy parameters by last value carried forward mostly biases towards patients appearing stronger or faster than they are, since it carries forward potentially a better value than the value at the time of the missed observation. Therefore, for this study, we will summarize how much data are missing, but do not expect to need to impute any data to accomplish the analyses as described. Details of handling missing data will be described in the Statistical Analysis Plan.

Missed assessments which occurred as a result of the COVID-19 pandemic will be entered on the COVID-19 Protocol Deviation Log by site personnel. It is anticipated that some or all assessments and laboratory tests required by the protocol schedule of events may be missed during the pandemic. Some of the missed assessments may be able to be collected at the next home or onsite visit. The missing data will be summarized in the Statistical Analysis Plan.

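### TEAE tables by dose level carry no exposure time, so the 40-to-80 mg/kg/week switch alone can make the dose groups differ when events are tabulated by treatment actually received

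*Combined protocol and SAP*

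**What the plan says.** Section 10.5.2 sets the grouping: "Treatment-emergent AEs (TEAEs) will be summarized by dose level". It then asks for two kinds of table.

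- **Patient level:** "How many patients had any TEAE, any SAE, highest severity of TEAE within a patient across all infusions", followed by the highest relationship, the strongest action taken with the drug, and the worst outcome.
- **Event level:** "Summaries will be done using the MedDRA coding by events and overall", by relationship, severity, intervention and outcome.

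Neither has a time denominator or a time axis. By contrast, Section 10.5.1 presents laboratory results, vital signs and ECG by dose level over time, and Section 10.5.4 does the same for cytokines and antibodies.

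The text on grouping points two ways. Section 10.5 says: "All safety assessments will be based on actual treatments received by participants". Section 10.1 has boys staying on their Study 201 dose and results summarised by that dose. Sections 3.1, 3.2.2.1 and 5.2 provide for the low-dose boys to move to 80 mg/kg/week under Amendment 10.

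Follow-up can also differ between boys. Section 3.3 ends it at about 192 weeks of treatment or at transfer to the long-term program, whichever comes first. Section 10.8 adds: "Patients lost to follow-up or withdrawn will be included in statistical analyses up to the point of their last evaluation".

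On exposure data, Section 5.5 says: "The amount of infusion received should be documented for all infusions". It also says that missed, delayed or incomplete infusions will be taken into account in the analysis, but not how.

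**The concern.** Safety is one of the two co-primary objectives (Section 10.5), and the study runs for up to 192 weeks. Over that time a crude count mixes how often events happen with how long a boy was watched. A row that nearly every boy enters cannot separate dose levels. An event count rises with weeks at risk even when the drug does nothing.

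Duration matters in the sponsor's own data. Section 1.3.4 gives a mouse NOAEL of 60 mg/kg/dose at 13 weeks and 15 at 26 weeks, although the monkey NOAEL was 60 at both 12 and 39 weeks. It also reports ureter carcinomas in three mice after 26 weeks of dosing. The protocol now includes urine cytology and renal ultrasound. The planned AE tables cannot show whether events become more frequent with time on drug, and a difference between their dose columns could come from unequal time alone.

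**Working it through.** The documents give no AE rate or expected count to reproduce. The time figures agree: Weeks 25 to 216 are 216 − 25 + 1 = 192 infusions, and 24 + 192 = 216.

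**1. Saturation of the any-TEAE row**

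Section 1.3.5.1 reports 10 boys treated for 12 weeks, "although all patients had at least one AE", with no SAEs.

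- Exact two-sided 95% lower limit for 10/10: 0.025^(1/10) = 0.6915.
- As a constant rate: −ln(1 − 0.6915)/12 = 0.0980 per week, or about 5.1 first events per patient-year.
- Incidence 1 − exp(−0.0980 × weeks): 90.5% at 24 weeks, 99.1% at 48, above 99.99% at 192.

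This holds at the lower limit, so the row carries almost no information. Rarer events behave differently. Over 192 weeks, doubling an assumed rate from 0.1 to 0.2 per year moves incidence from 30.9% to 52.2%. Doubling from 1 to 2 per year moves it only from 97.5% to 99.9%. For SAEs, 0/10 in Phase I has an upper limit of 1 − 0.6915 = 30.8% over 12 weeks, so saturation cannot be presumed.

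**2. Patient-time per dose under the actual-treatment rule**

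Assumptions: 8 boys per cohort (the plan says about 16 in all), full follow-up, and all eight low-dose boys switching at Week W. Section 3.2.2.1 words the increase as something the investigator can do, so a switch by all eight is itself an assumption. The documents give no switch week. Table 1, notes 6 and 8, place the first assessment after Amendment 9 approval at Visit 133 or 145, and Sections 3.1 and 3.3 tie Week 193 to the start of the Amendment 10 visits. I therefore use Weeks 145 to 193.

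- Patient-weeks at 40: 8 × (W − 25)
- Patient-weeks at 80: 8 × 192 + 8 × (217 − W)

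| Switch week | At 40 | At 80 | Ratio 80/40 | Weeks per boy, 40 (8 boys) | Weeks per boy, 80 (16 boys) |
|---|---|---|---|---|---|
| 145 | 960 | 2112 | 2.20 | 120 | 132 |
| 169 | 1152 | 1920 | 1.67 | 144 | 120 |
| 193 | 1344 | 1728 | 1.29 | 168 | 108 |

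Under one common rate, event counts follow the ratio column. At an assumed 0.5 events per patient-year, expected events (40 vs 80) are 9.2 vs 20.3 for a Week 145 switch and 12.9 vs 16.6 for Week 193.

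**3. Patient-level incidence under the same rule**

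The 80 column holds 16 boys: 8 with 192 weeks and 8 with 217 − W weeks.

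- Week 193, 0.5 per year: at 40, 1 − exp(−0.5 × 168/52) = 80.1%. At 80, the mean of 84.2% (192 weeks) and 20.6% (24 weeks) is 52.4%.
- Week 145, 0.1 per year: 20.6% at 40 vs 21.9% at 80.
- Week 145, 0.5 per year: 68.5% vs 67.1%.

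So with no drug effect and a Week 193 switch, the event table shows more events at 80 while the patient table shows fewer affected boys at 80. For a Week 145 switch the patient-level artefact is small and its sign depends on the rate.

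**4. Original-cohort attribution**

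Planned time is 192 weeks in both cohorts, a ratio of 1.0. Only early exit, withdrawal or missed doses then unbalance it. For size: at 0.5 per year, a boy followed for 96 weeks has a 60.3% chance of an event, against 84.2% at 192 weeks.

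**The case against.** The strongest reply is that Section 10.1 summarises by Study 201 dose. On that reading planned time is equal, and nothing in the documents suggests that transfer or withdrawal differs by cohort. This stands. A reader might infer that raw counts are non-comparable however switched boys are attributed; the documents do not support that. But the cohort reading puts events at 40 and at 80 in one low-dose column, and it sits uneasily with the actual-treatment rule in Section 10.5.

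A reader might also infer that all AE tables saturate. They do not: SAEs, severe events and uncommon terms need not, and Phase I had no SAEs and nothing at Grade 3 or above. A larger imbalance, such as 3.0 for a Week 121 switch, is tempting too. It does not fit Table 1, where assessments under the preceding amendment first fall at Visit 133 or 145. Comparing only the low-dose boys' weeks at 40 with 192 weeks for boys always on 80 would also mislead, because it drops the switched boys' own weeks at 80.

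Other mitigations are real. Renal laboratory values are summarised over time, all AEs are listed with onset dates (Section 9.5.1), and the DSMB sees safety data every six months. The list in 10.5.2 need not be exhaustive, and Section 10.1 defers detail to an SAP whose separate text is not in the file reviewed. These points limit the harm. They do not put a denominator under the planned AE tables.

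**Conclusion.** The point holds as a recommended change to Section 10.5.2. The planned AE tables have no exposure time and no time interval. The any-TEAE row will be near 100% in each group. If events are tabulated by treatment received, equal true rates would give 1.29 to 2.20 times as many events at 80 as at 40, and patient-level incidence can be distorted in either direction. If tabulated by original cohort, the built-in imbalance disappears and what remains is the mixing of doses plus any early exit or missed dosing.

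The figures assume 8 boys per cohort, all eight low-dose boys switching in the same week between 145 and 193, full follow-up and constant rates; the 30-day TEAE tail after the last dose is ignored. The tables are descriptive, so the effect is on how the co-primary safety objective is read and not on a formal test.

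**What to change.** Keep the planned patient-level and event-level tables, and add the following to Section 10.5.2 or the SAP, for TEAEs, SAEs and renal events (the renal and urinary items of Section 9.5.3 are a ready definition):

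- Patient-years of exposure and events per patient-year, by the dose being received at onset, with post-switch time and events assigned to the dose received.
- Intervals that allow for repeat events within a boy, such as robust variance or a bootstrap that resamples boys. With 8 to 16 boys these are approximate and should be labelled so. Plain exact Poisson intervals suit first events only. Any contrast between doses must recognise that switched boys contribute to both.
- Summaries by time on drug, in intervals of 24 weeks or wider. Eight boys over 24 weeks give 8 × 24/52 = 3.7 patient-years, so an empty cell still has an upper 95% limit of about −ln(0.025)/3.7 = 1.0 per patient-year.
- Time to first SAE and to first renal event, censored at exit.
- One sentence reconciling Sections 10.1 and 10.5 on the dose column to which post-switch events belong.

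Infusion amounts, missed doses and AE onset dates are already collected, so the cost is SAP wording and programming. The downside is more tables, with wide intervals.
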